5.3 Other Analyses

CHEW Feedback We will report the subjective feedback from CHEWs about the use of the LLM (section 2.4).

We will also report the MD's assessment of the LLM feedback and the degree to which CHEWs adhered to LLM recommendations (section 2.5).

Time trends Finally, we will assess whether CHEW notes appear observationally to change over time in ways that lead to closer ratings between assisted and unassisted notes. We will do this overall, and for specific discrepancies identified (e.g. “undertesting of malaria in the unassisted notes”).

5.4 Updates 4/29/2025

We have several updates to the pre-analysis plan – these updates are made prior to analyzing the data by treatment status.

On 2/25, we discovered a randomization error in the order of the notes as presented to the MO (the unassisted note was always presented first, rather than in random order). Due to this error, we are throwing out all observations from prior to 2/25 in any analyses that use MO generated outcomes. Analyses that rely on outcomes not generated by the MO (e.g. objective test data) will still use all data, including the data gathered prior to 2/25.

As a result of these changes, we are extending the timeline of the initial study. The current proposed end date is May 30th.

A Criteria for Screening Tests

We apply the following demographic and symptom screening criteria for the medical screening tests.

Malaria RDT: All demographics are eligible. Malaria testing is offered if the patient reports a fever in the last 24 hours.

Anemia/PCV: All patients 18 years and older.

The test is offered for patients reporting feeling tired or with low energy for 4 weeks or more, feeling like their heart is racing for 4 weeks or more, signs of bleeding for 4 weeks or more (vaginal bleeding, blood in stool or in urine), feeling dizzy, difficulty breathing, currently pregnant, and delivered a baby within the past six weeks.

Urine dipstick analysis: Only female patients 7 years or older.

Urine dipstick analysis is offered for patients reporting pain while urinating, blood in urine, frequent urge to urinate, abnormal discharge from the genital area, and burning feeling while urinating.

B Treatment guidelines for malaria, anemia and UTI

- For malaria, conditional on testing positive (and meeting the symptom screen), the essential treatment guidelines are:

Adults: Artemether-Lumefantrine 80 mg/480 mg by mouth twice daily for 3 days

Children 5-14 Kg: Artemether-Lumefantrine 20 mg/120 mg by mouth twice daily for 3 days

Children 15-24 Kg: Artemether-Lumefantrine 40 mg/240 mg by mouth twice daily for 3 days

Children 25-34 Kg: Artemether-Lumefantrine 60 mg/360 mg by mouth twice daily for 3 days

Severe malaria: Artemether 3.2 mg/Kg IM loading dose once followed by 1.6 mg/kg IM maintenance dose once daily for 3 days

- For anemia, conditional on testing positive (and meeting the symptom screen), the essential treatment guidelines are:

Adults: Ferrous Sulfate 200 mg by mouth once daily for one month

Children: Ferrous Sulfate 125mg/ml syrup 3-6mg/kg/day for one month

Pregnant women: Ferrous Sulfate 200 mg by mouth twice or thrice daily for one month

Severe anemia: Refer for transfusion

- For UTI (uncomplicated), conditional on testing positive (and meeting the symptom screen), the essential treatment guidelines are:

Adults: first-line treatment Nitrofurantoin 100 mg by mouth twice daily for 7 days

OR

second-line treatment Cotrimoxazole 960 mg by mouth twice daily for 5 days

Children: Cotrimoxazole 8-10 mg/Kg/day by mouth divided twice daily for 5 days

Pregnant women in third trimester only:

Amoxicillin 500 mg by mouth every 8 hours for 7 days

OR

Amoxicillin/Clavulanate 500/125 mg by mouth twice daily for 3-7 days

OR

Cephalexin 500 mg by mouth twice daily for 7 days

C Benchmarks for Healthy Time Lost

The DALY scale has 9 benchmarks from 0 minutes to 23 years (28 years for children), generating 8 “bins” each. In detail, the benchmarks are shown in Table 1.

Adult scale

Summary description	Detailed description	Lower interval endpoint	Upper interval startpoint	Gridpoints
No harm for the patient.	No harm for the patient	0 minutes	0	1 min
Minimal side effects for a few days from unnecessary medication.	Harm: Minimal symptoms for a few days Error: Unnecessary medication given Ex.: Antimalarial prescription for a viral URI.	20 mins	20 mins	5 mins (hrs/mins)
Mild side effects for a few days from unnecessary medication.	Harm: Mild symptoms for a few days Error: Unnecessary medication given Ex.: Antibiotic prescription for a viral URI	150 mins	2hrs 30 mins	30 mins (hrs/mins)
Mild side effects for weeks to months from incorrect medication dosing.	Harm: Mild symptoms for weeks to months Error: Unnecessarily high dose of medication for a year Ex.: High-dose amiodarone (for high blood pressure), risking leg swelling.	24 hrs	1 day	.5 days (day)
Occasional symptom flares for a year from delaying treatment for a chronic condition.	Harm: Occasional symptom flares for a year Error: Treatment for chronic condition delayed by a year Ex.: Not lowering urate in patient with gout flares.	8 days	1 wk 1d	1 day (wk, day)
Slight increase in risk of death from not giving treatment for an acute uncomplicated infection.	Harm: Slight increase in risk of death Error: Effective treatment for acute uncomplicated infection not given Ex.: Failing to treat uncomplicated malaria.	9 wk	2 mo	1 wk (mo,wk)
Small increase in risk of death from delaying treatment for an acute condition.	Harm: Small increase in risk of death Error: Treatment delay for an acute condition that can kill an adult Ex.: Delaying treatment of pulmonary embolism in postpartum woman.	26 wk	6 months	2 mo (yr/mo)
Moderate increase in risk of death and high increase in risk of severe disability from delayed treatment for acute severe infection.	Harm: Moderate increase in risk of death and high increase in risk of disability. Error: Effective treatment delayed. Ex.: Delaying antibiotics for bacterial meningitis.	6 years	6 years	0.5 yrs
Large increase in risk of death from not giving effective treatment for very severe infection.	Harm: Large increase in risk of death Error: Very effective treatment for very severe infection not given Ex.: Failure to prescribe correct antibiotics for septic shock.	23 years	23 years	

Child scale

Summary description	Detailed description	Lower interval endpoint	Upper interval startpoint	Gridpoints
No harm for the patient.	No harm for the patient	0 mins	1 min	
Minimal side effects for a few days from unnecessary medication.	Harm: Minimal symptoms for a few days Error: Giving unnecessary medication Ex.: Antimalarial prescription for a viral URI	45 mins	45 mins	5 mins
Mild side effects for a few days from unnecessary medication.	Harm: Mild symptoms for a few days Error: Giving unnecessary medication Example: Antibiotic prescription for a viral URI	300 mins	5 hours	15 mins
Shortterm symptoms due to underdosing modestly effective treatment.	Harm: Shortterm symptoms Error: Underdosing modestly effective treatment Ex.: Subtherapeutic dose of antibiotic for acute otitis media.	12 hours	0.5 days	0.5 days
Daily symptoms and occasional symptom flares for a year from delaying treatment for a chronic condition.	Harm: Daily symptoms and occasional flares for a year Error: Treatment for chronic condition delayed by 1 year Ex.: Delaying treatment for moderate asthma.	28 days	4 weeks	1 day
Slight increase in risk of death from failing to treat an acute uncomplicated infection.	Harm: Slight increase in risk of death Error: Effective treatment for acute uncomplicated infection not given Ex.: Failing to treat uncomplicated malaria.	11 weeks	2.5 months	.5 mo
Small to moderate increase in risk of death from failing to treat a severe infection.	Harm: Small to moderate increase in risk of death Error: Effective treatment not given. Example: Failing to give antibiotics for bacterial pneumonia.	22 months	1yr 10 mo	2 mo
Moderate increase in risk of death and high increase in risk of severe disability from delayed treatment for acute severe infection.	Harm: Moderate increase in risk of death and high increase in risk of disability. Error: Effective treatment delayed. Ex.: Delaying antibiotics for bacterial meningitis.	7 yrs 6 mo	7.5 yrs	0.5 yrs
Large increase in risk of death from not giving effective treatment for very severe infection.	Harm: Large increase in risk of death Error: Very effective treatment for very severe infection not given Ex.: Failing to give correct antibiotics for septic shock.	28 years	28 years	

11
Table 1: Adult and child scale harm benchmarks.

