2.2 Patient EMR data

All patient data is saved in the EMR. At various points, this data is collated into SOAP notes (structured text files describing subjective and objective signs and symptoms, the provider's assessment (diagnosis), and the treatment plan).

The SOAP notes that are saved are:

- “Unassisted” SOAP note created on initial patient consultation and submitted to LLM: contains care plan conditional on results of requested medical tests, randomly labeled SOAP A or B
- “Assisted” SOAP note created after LLM feedback was received: conditional care plan, randomly labeled B or A
- Conditional MO SOAP note: conditional care plan, created by MO prior to receiving laboratory test results
- Patient discharge SOAP note: patient care plan created by MO after receiving laboratory test results and communicated to patient
- Final MO SOAP note: patient care plan created after reviewing study medical tests (malaria, anemia, UTI).

In addition, we have the values of individual EMR fields that make up these SOAP notes, e.g. test results, diagnoses, prescriptions, etc., including patient demographics and vital signs.

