2.3.1 The MO's SOAP note evaluation

The evaluation focuses on treatment errors in the SOAP note that could cause some form of (medical) harm to the patient.

For each SOAP note, the MO first takes stock of qualitative differences between the CHEW's and the MO's plan, then assesses the type of harms for the patient from any errors, and finally rates the SOAP note on a scale for “healthy time lost”. The MO is blinded to whether the SOAP note is LLM-assisted or unassisted and rates SOAP Note A before seeing SOAP Note B.

Deviations from the MO's SOAP The MO is asked to assess for each SOAP note whether medical tests ordered were necessary or clinically useful vs. unlikely to be useful, whether there are missing or incorrect/unnecessary diagnoses, and whether there are missing or incorrect/unnecessary treatment plan elements.

Types of harm incurred The MO is asked to assess any short-term harm (additional symptoms or discomfort for some period), and any long-term serious harm (risk of impairment, death etc.) from the treatment plan in the SOAP note.

Measuring Healthy Time Lost in DALY The MO also provides an overall rating that is intended to reflect the “healthy time lost” from any errors in treatment in the SOAP note. For each assessment and plan constructed by a CHEW (with or without LLM advice), an MO will assess the expected magnitude of healthy life that would be lost if the CHEW plan were implemented instead of the MO's plan. Healthy time is measured in units of disability-adjusted life year (DALYs), which reflect both length and quality of life. Losing one DALY is equivalent to losing a year of life in perfect health, or two years of life experienced in an unhealthy state with a utility weight of 0.5, etc.

MOs estimate DALY losses with the aid of a DALY scale. The DALY scale consists of a set of cutoff points that were calibrated using benchmarks of expected DALY loss for clinical mistakes relevant to local medical practice. Because the DALY consequences of permanent harm (death or disability) are higher for children than for adults, and because different clinical mistakes are relevant for children and adults, we provide a separate DALY scale for the evaluation of CHEW notes for patients who are children (under 18) and patients who are adults.

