3.1 Estimation

The primary analysis estimates the effect of LLM assistance on the four outcomes above, all broad indicators for the overall quality of care provided. Every outcome is measured both for assisted and unassisted SOAP notes. We will estimate

$$Y_{it} = a_i + bT_k + cX_{ik} + \epsilon_{ik}$$

where i is the patient (or patient-test combo in 3.5) and $k = \{A, B\}$ is the SOAP note. Y_{ik} is the outcome, a_i is a patient (patient-test) fixed effect, T_k is an indicator for “assisted” and X_{ik} are optional controls for order effects and unblinding (see next section).

We will calculate robust standard errors. In addition, we will separately report p-values using the Benjamini Hochberg procedure for controlling false discovery rates at $p = 0.05$. This will lead to a conservative estimate of the power of our statistical tests. We will also separately report means, standard deviation, and number of observations of each variable for the assisted and unassisted notes.

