5.1 Blinding

We will conduct checks to control for the possibility that imperfect blinding to the intervention (i.e. MO knowledge whether a patient note was “LLM assisted” or not) is impacting our results.

- We measure each MO’s beliefs about whether a given patient note was LLM-assisted with a survey question. We will analyze whether MO beliefs about whether a note was LLM assisted are predicted by true LLM assistance status.
- As a robustness check, we will control for MO beliefs about LLM assistance and for any order effects (i.e. identity of note A vs. B) in the main analysis.
- Ex post, if we find that MOs can reliably predict whether a note was LLM assisted, we will seek to identify whether there are specific outcome-irrelevant features of notes which aid in this prediction, and may run additional robustness checks on a subset of patients where this feature was absent, so blinding is better maintained.

Bias in the difference in evaluation between notes A and B can arise if the MO (i) correctly guesses which note is assisted by the LLM, and (ii) systematically rates notes more highly if they are assisted by the LLM, but *not* due to higher quality of care/true lower harm to the patient.

For the first note that each MO sees (note A), we elicit a “raw” evaluation score prior to seeing note B. This score is then amended into an “adjusted” final evaluation (the reason for the update is the potential for learning about note A, given the cognitively demanding task of the MO: for example, only when shown the highlighted differences between the two notes may the MO detect an error in note A.) In an ideal world, the “adjusted” rating simply reflects the MO’s evaluation given full information. This is the measure we use in most of our analysis. However, the “raw” score provides an opportunity for another blinding check, under the assumption that blinding is more problematic for note B than note A.

If this is the case, a cleaner but noisier estimate of our main effect can be obtained by using an across-patient comparison of the “raw” scores of assisted and unassisted SOAP notes A. This regression will be identical to our baseline specification, but omitting the patient fixed effects.

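### Section 5.4 cuts the MO-rated data at the day the order error was discovered and does not state when random order went live, so a few unassisted-first pairs may remain in primary outcomes 1 to 3

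*SAP*

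**What the plan says.** Section 2.2 makes the A/B label of the two CHEW notes random: the unassisted note "contains care plan conditional on results of requested medical tests, randomly labeled SOAP A or B". Section 2.3.1 says that the MO "rates SOAP Note A before seeing SOAP Note B", so the label fixes the rating order.

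Section 5.4 reports that this failed: "the unassisted note was always presented first, rather than in random order". It dates the discovery: "On 2/25, we discovered a randomization error in the order of the notes as presented to the MO". The remedy is: "we are throwing out all observations from prior to 2/25 in any analyses that use MO generated outcomes". Test-based outcomes are exempt: "Analyses that rely on outcomes not generated by the MO (e.g. objective test data) will still use all data".

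Section 5.4 gives no date or time for the correction. It does not say that the retained pairs were checked against the order in which they were shown. It does say that the updates were made before any analysis by treatment status, and it proposes May 30th as the new end date.

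On order in the model, Section 3.1 treats controls for order effects as optional. Section 5.1 states: "As a robustness check, we will control for MO beliefs about LLM assistance and for any order effects".

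**The concern.** A fault cannot be corrected before it is found, so 2/25 is the earliest day on which random order can have started. The rule keeps that day in full. It is exactly right if random order was working before the first MO rating on 2/25. Otherwise it keeps pairs that were still shown unassisted-first.

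The authors thought the fixed order serious enough to discard all earlier MO-rated data and extend the study. A boundary that may let some of the same pairs back in does not fully carry out that decision. Position can plausibly affect the ratings. Note A is scored before Note B is seen and is then amended (Section 5.1). Note B is reviewed only if the MO answers yes or unsure on meaningful differences (Section 3.4).

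Patient fixed effects do not remove a position effect. Balance between assistance and position exists only across pairs, and a surplus of unassisted-first pairs tilts it. Any error, severe error and better plan (outcomes 1 to 3) all rest on MO ratings. The test-based outcome 4 does not depend on the order shown to the MO.

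**Working it through.** The SAP has no figure to reproduce here. The check is a reading of the rule, followed by an illustration of size.

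**Inputs from the SAP.** Discovery on 2/25, exclusion before 2/25, and proposed end on May 30th (all Section 5.4). The year is taken as 2025 from the date of the SAP. From 2/25 to 5/30 inclusive is 4 + 31 + 30 + 30 = 95 calendar days, or 4 + 21 + 22 + 22 = 69 weekdays.

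**Assumptions, not in the SAP.** Lag L between the start of 2/25 and go-live; even accrual over the period; an additive order effect d (Note B minus Note A) of 10 percentage points.

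**Formulas.** Let f be the share of retained pairs still shown unassisted-first because of the fault.

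- f = L/95 (calendar days) or L/69 (weekdays).
- P(assisted shown second) = 0.5 + 0.5f.
- The assisted-minus-unassisted difference within a pair is b + d if the assisted note is second and b − d if it is first. Its mean is b + d(2P − 1) = b + f·d.
- So the bias without an order term is f·d. It does not depend on the number of pairs retained.

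**Results, calendar-day accrual:**

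| Lag (days) | f | P(assisted second) | Bias at d = 10 points |
|---|---|---|---|
| 0 | 0 | 0.500 | 0 |
| 0.5 | 0.5% | 0.503 | 0.05 |
| 1 | 1.1% | 0.505 | 0.11 |
| 3 | 3.2% | 0.516 | 0.32 |
| 7 | 7.4% | 0.537 | 0.74 |
| 14 | 14.7% | 0.574 | 1.47 |

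With weekday accrual, one day is 1/69 = 1.4% and three days are 3/69 = 4.3%, with biases of 0.14 and 0.43 points. Over both conventions, a lag of one to three days gives f of 1.1% to 4.3% and a bias of about 0.1 to 0.4 points. At an assumed 5 points for d, each bias halves.

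**Simulation.** The check used 500 pairs, 2,000 repetitions, d = 0.10, no true effect, and a within-pair standard deviation of 0.6 (assumed). Monte Carlo error of each mean is about 0.6/√500/√2000 = 0.0006.

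| f | Expected f·d | Without order term | With order term |
|---|---|---|---|
| 0.011 | 0.0011 | 0.0001 | −0.0008 |
| 0.074 | 0.0074 | 0.0084 | 0.0011 |
| 0.147 | 0.0147 | 0.0148 | 0.0002 |
| 1.000 | 0.1000 | 0.1004 | not identified |

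The results agree with f·d within simulation error. An order term brings the bias to about zero whenever both orders occur. The last row is the situation before 2/25, where no model can separate order from assistance.

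**The case against.** The strongest reply is that nothing in the SAP shows that discovery and go-live differ. Section 5.4 was written on 4/29, about two months later, describes the fault in the past tense, and chooses 2/25 as the boundary. A correction before the first rating that day fits the text, and the bias is then zero. This stands: a reader might infer that the retained data are contaminated, and the document does not support that. What remains is that the rule is tied to the wrong event and the SAP gives no means of confirming that it worked.

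Second, the robustness check with an order term removes an additive position effect. This also stands, and it limits the stakes. It does not protect the primary estimate by default, because Section 3.1 leaves that term optional.

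Three stronger readings are tempting and should not be drawn.

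- **Position confounding in the raw Note A check (Section 5.1).** That check compares only first-shown notes across patients, each scored before Note B is seen. Position is constant. Retained unassisted-first pairs would only add unassisted notes from the first days, a slight calendar imbalance.
- **A larger affected share.** Assuming ten patients a day, three affected days and 350 retained pairs gives 30/350 = 8.6%, or about 0.9 points. These inputs conflict under even accrual: 350 pairs is 350/95 = 3.7 per calendar day or 350/69 = 5.1 per weekday. Ten a day would give 690 to 950 pairs.
- **Pairs ordered before 2/25 but rated later.** Section 5.4 does not say which date places an observation before 2/25. However, no section states a lag between visit and rating, or that the order was fixed before it was shown to the MO. This route remains speculative, although the fix below closes it.

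**Conclusion.** The point holds as a minor one. The exclusion is set at the discovery date, keeps 2/25 itself, and is not tied to the go-live of random order. Unless random order was live before the first MO rating on 2/25, some unassisted-first pairs remain in primary outcomes 1 to 3. Contamination is unproven.

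For a lag of one to three days, the likely size is 1.1% to 4.3% of retained pairs and a bias of about 0.1 to 0.4 percentage points without an order term. This rests on even accrual to 5/30, an additive order effect of 10 points, and the assumed lag, none of which the SAP gives. A lag of one or two weeks would raise the bias to about 0.7 or 1.5 points on calendar-day accrual. The case for acting is the low cost and the three primary outcomes that the rule protects, not a large expected bias.

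**What to change.** Replace the date rule in Section 5.4 with wording such as: exclude from all analyses of MO-generated outcomes every pair whose display order was generated before the corrected randomisation went live, as shown by the system timestamp or the logged order. State that date and time. Report the assisted-first share by day in the retained pairs, to show that it is near 50% from the first retained day, allowing for small daily counts.

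The cost is a log check, one or two sentences in the SAP, and possibly a few lost pairs. If random order was live in time, no pair is lost and the cut-off is documented. The change should be made before any analysis by treatment status, the condition under which Section 5.4 says its updates were made, so that the cut-off cannot appear to have been chosen with the results in view.
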